To evaluate the impact of these three interventions, we will conduct a 3x2 factorial RCT across two sub-districts in rural Bangladesh. The two information treatments will be cross randomized with the one mental health intervention. The mental health intervention will be randomized at the Union Health and Family Welfare Centre (UHFWC) level (there are 20 total UHFWCs across the 2 Upazilas), stratified by sub-district, and allocated at a 1:1 ratio. We will then randomly select 120 villages within subdistricts, stratified by UHFWC, to participate. The information interventions will be randomized at the village level, stratified by UHFWC, with 40 villages receiving information and enrolment support for government programs, 40 villages receiving additional information on the importance of early life conditions, and 40 control (no information) villages. Eligible participants will be pregnant women and mothers with young children aged 6 months or younger. We will aim to recruit 22 women per village to be part of the study sample.

We will use two types of data, (i) the data from the digital information system of Kapsasia Model built at the sub-district level by the local government, which we call *administrative data*, and (ii) household and individual survey data including elicitation of maternal beliefs of prospective and existing mothers that we will collect as a part of the study, which we call *household survey data*. This survey will be conducted on the sample of 22 women per village for a **total sample of 2,640 women**. The administrative data include information (e.g., age, education, occupation, mobile phone number, pregnancy status, birth outcomes, number of children) on *all* registered newly married couples in our study area, including the 22 women per village in our study sample, and will identify key outcomes such as pregnancy status and birth outcomes. We will conduct a baseline survey with an endline 10 months later, and we plan to conduct a midline survey by phone (which will likely be funded using internal funds² from the University of Sydney and University of Melbourne) to measure parental inputs in the in utero period. The schedule of enrolment, intervention and evaluations is given in Figure 1.

² They have not been mentioned in the budget as no firm commitment has been received yet.

The study schedule	Study period													
	Baseline							Midline				Endline		

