	1st month	2nd month	3rd month	4th month	5th month	6th month	7th month	8th month	9th month	10th month	11th month	12th month	13th month	14th month
Enrolment														
Eligibility Screening	X													
Consent collections		X												
Randomization & allocation to treatments and control group			X											
Interventions/ Treatments														
1. Information and enrolment support to govt. programs				X	X	X	X	X	X	X	X			
2. 1 + Information on the importance of early life conditions				X	X	X	X	X	X	X	X			
3. Psychological counselling				X	X	X	X	X	X	X	X			
Evaluations														
Compliance Check - if individuals and groups assigned to treatments and controls are in fact complying to the assignment					X	X	X	X	X	X	X			
Household characteristics and other basic information, houses, lands, and asset ownership, economic activities and employment, beliefs, women mental health, preferences		X										X		
Parents time and monetary investment on children								X						
Anthropometry & health, children’s mental health and development, take up of health care services, participation in social transfers/safety net programs, parenting style, parents time and monetary investment on children, food intake/share, food insecurity & non-food expenditures, women empowerment, intimate partner violence													X	
Data Analysis														X X
Report Writing/ Publication														X X

Figure – 1: Schedule of enrolment, intervention, and evaluations

Power Calculation: Given the sample sizes above and accounting for the varied clustered design, we would be powered to detect a Minimum Detectable Effect (MDE) size of 0.31 of a standard deviation (SD) change for the mental health intervention (randomized at the Health Centre (UHFWC) level with the conservative estimate of 20 centers). For the information arms, we would be powered to detect a 0.19SD change for either of the information interventions (main effects only). As benchmark for the MDEs on mental health interventions, Rahman et al. (2008) found that a mental health intervention similar to the one proposed here improved mothers’ mental health by 0.70SD, while Sikander et al. (2019) found that a more scalable, peer-delivered version of the intervention increased mothers’ mental health by 0.30SD. A tele-counseling intervention in Bangladesh improved mental health by 0.65SD (Vlassopolous et al. (2021)).

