9. OUTCOMES

Our primary outcomes include measures of women's empowerment, parental investment, mother's physical and mental health, and intimate partner violence. Our secondary outcomes focus on the child and include measures of physical health and cognitive and socio-emotional development. We list the specific primary and secondary outcome variables below.

Primary outcomes: Women's empowerment (women's agency in fertility planning, personal expenditures and expenditures on children, children and household investment decisions, savings accounts, and participation in social programs and local leaderships); Women's beliefs (about importance of early life conditions, self-efficacy in parenting, beliefs about modifiability of child skills); Parental Investment (time, monetary, and warmth); Physical health (self-

reported physical health, body-mass index, and mid-upper arm circumference (MUAC)); Mental health (PHQ-9 a screener for depression, GAD-7 a screener for anxiety); IPV; and Stress (Cohen Stress Scale, Biomarkers of stress using hair samples³).

Secondary outcomes: Child's health at birth (birth weight and low birth weight); Developmental outcomes (Bayley Scales of Infant and Toddler Development that captures children's cognitive, language, motor, adaptive); Health (weight-for-length, length-for-age, acute respiratory illnesses); Stress (Biomarkers of stress from hair samples).

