³ We plan to collect biomarkers of stress from mothers and their infants. Using hair samples, we can extract HPA axis hormones such as cortisol. Hair-derived biomarker measurement indicates HPA axis activity over the course of months (analytes in each centimeter of hair approximate hormone secretion over one month), and thus more accurately reflect chronic hormone secretion (see Baranov et al. 2022 for a discussion and an example of successful hair cortisol measurement with mother and child dyads in Pakistan). Hair sample collection will be funded with this proposal but further funding will be sought for laboratory extraction of analytes. Hair samples are easily storable and stable for 1-2 years.

done in two steps – firstly, a small team independent of the survey firm will reinterview about 5% of the respondents selected randomly. This data will be matched with data collected by enumerators employed by the survey firm. Secondly, all field data will be matched with administrative data on key variables. Based on the above, a daily report will be generated specific to enumerator, which will be followed up by the field supervisors/ research assistants that we will employ.

Data Safety and Access to Data: All electronic data will be anonymized, encrypted, and stored at a secured server owned by the University of Sydney. The access to the server will be password protected and will be limited to the research investigators only. Similarly, all scanned copies of the consents will be similarly stored in a secured server, where access will be password protected, and only authenticated users will be allowed to access them. All hard copies of the consent forms stored in the local collaborator's office in Dhaka will be destroyed once the project is completed and it is no longer required to keep the hard copies.

All individual identifiers will be removed and will be replaced with codes, which would be used in case the research team plans to re-identify the participants. Such re-identification will be arranged with the Kapasia Model of Maternal and Child Health authority and will give the option to conduct long-term follow studies that track the effects of early intervention on human capital accumulations in adulthood. Such a study would be of significant interest to many policy makers and researchers alike.

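### Empowerment, IPV and maternal anthropometry are primary but not scheduled at the pre-randomisation survey, the stress outcomes appear in no row of Figure 1, and the hair assay is not yet funded

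*Protocol*

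**What the plan says.** Protocol Section 9 itemises seven primary domains: empowerment, beliefs, parental investment, physical health (self-report, BMI, MUAC), mental health, IPV and stress. The stress item reads "Stress (Cohen Stress Scale, Biomarkers of stress using hair samples".

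In Figure 1 (Section 6) randomisation is in month 3. The only outcome row marked before that is the general survey row, marked at months 2 and 12. After the household items it lists "economic activities and employment, beliefs, women mental health, preferences". The row that ends "food intake/share, food insecurity & non-food expenditures, women empowerment, intimate partner violence", and that begins with anthropometry and health, is marked at month 13 only. Parental time and money are marked at month 8 and again within the month-13 row. No row names the stress scale or hair samples.

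Section 10 makes the baseline interview face-to-face, and Section 11 places it in month 2, ahead of allocation. Footnote 3, attached to the hair samples in Section 9, says that collection will be funded but "further funding will be sought for laboratory extraction of analytes".

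Counselling is randomised by health centre: "there are 20 total UHFWCs across the 2 Upazilas), stratified by sub-district, and allocated at a 1:1 ratio".

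**The concern.** An in-person interview with every participant is already planned before allocation, but as scheduled it does not collect three primary measures that could be taken then. Once month 3 has passed they cannot be recovered, and no analysis plan can adjust for values that were never recorded.

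This matters most for counselling. With ten centres per arm, chance differences between arms at the start can be a sizeable fraction of the effect that the trial is built to detect. For these outcomes such a difference could be neither seen nor adjusted for on the outcome itself.

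The stress domain raises a second issue. The schedule does not say when it is measured, and one of its two components depends on money not yet secured. The set of primary outcomes is therefore not settled at randomisation.

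**Working it through.** **1. Primary domains against Figure 1**

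| Primary domain (Section 9) | Months marked | Before month 3? |
|---|---|---|
| Beliefs | 2, 12 | yes |
| Mental health | 2, 12 | yes |
| Empowerment | 13 | no |
| IPV | 13 | no |
| Physical health (BMI, MUAC) | 13 | no |
| Parental investment | 8, 13 | no, but not measurable for women without a child |
| Stress | not named | not shown at any time |

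The clear and avoidable gaps are empowerment, IPV and maternal anthropometry.

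**2. Inputs**

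- Centres: 20 at 1:1, so G = 10 per arm.
- Women: "We will aim to recruit 22 women per village to be part of the study sample". 120 × 22 = 2,640, and 2,640 / 20 = 132 per centre on average.
- Villages: 40 per information arm ("40 villages receiving additional information on the importance of early life conditions, and 40 control (no information) villages").
- The ICC, alpha, power and covariate R² behind the stated minimum detectable effects (MDEs) are not given. I assume two-sided 5%, 80% power and no covariates.

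**3. The plan's own MDEs**

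MDE = (t₀.₉₇₅ + t₀.₈₀) × √[2(1 + (m − 1)ICC)/(G m)].

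Because the ICC is not stated, the figures cannot be strictly reproduced, but the implied ICC can be solved for:

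- Counselling, 0.31 SD (G = 10, m = 132): ICC 0.048 with t on 18 df, or 0.054 with normal quantiles.
- Information, 0.19 SD (G = 40, m = 22): ICC 0.046 with t on 78 df, or 0.049 with normal quantiles.

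A single ICC of 0.0475 with t gives 0.310 and 0.191. The two figures agree with each other and fit a calculation without baseline adjustment. An ICC of 0.05 is therefore a reasonable working value; I use 0.02 to 0.10 as the range.

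**4. Chance imbalance between counselling arms**

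SE = √[(2/10)(ICC + (1 − ICC)/132)]

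| ICC | SE (SD units) | P(difference above 0.2 SD) |
|---|---|---|
| 0.02 | 0.074 | 0.7% |
| 0.05 | √[0.2 × (0.05 + 0.95/132)] = 0.107 | 6.1% |
| 0.10 | 0.146 | 17.1% |

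The probabilities are two-sided normal and apply per domain. A difference of 0.2 SD is 0.2/0.31, or about two thirds of the stated MDE. Stratification by sub-district is ignored here and could lower these values somewhat.

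For one information arm against control at ICC 0.05, SE = √[2 × (1 + 21 × 0.05)/880] = √(4.1/880) = 0.068. The problem is smaller there.

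**5. What adjustment could gain**

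If baseline and endline correlate r at both centre and woman level, the MDE is multiplied by √(1 − r²):

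| r | 0.31 SD becomes |
|---|---|
| 0.3 | 0.296 |
| 0.5 | 0.268 |
| 0.7 | 0.221 |

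The protocol gives no value for r, and the centre-level correlation dominates. At ICC 0.05 the variance per centre mean is 0.05 + 0.95/132 = 0.05 + 0.0072 = 0.0572, so 0.05/0.0572 = 87% lies between centres. If r = 0.7 held among women within centres and were zero between centres, the variance would be 0.05 + 0.0072 × (1 − 0.49) = 0.0537. The MDE ratio is √(0.0537/0.0572) = 0.97, a gain of about 3%.

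**The case against.** Measuring some outcomes only at endline is a legitimate randomised design. Chance imbalance does not bias the comparison, and a standard error that respects the clusters already allows for it. This stands: the loss is precision and the ability to check balance, not validity.

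A reader might infer that five of the seven primary domains lack a baseline. The table can be counted that way, but as a criticism it is too strong. Newly married and pregnant women are eligible, and those without a child cannot report parental investment. The stress scale may be meant under women's mental health, which is scheduled in month 2. Figure 1 omits stress at every time point, so its silence at month 2 is weak evidence about the baseline.

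The mental health outcome, against which the protocol benchmarks its counselling MDE, does have a baseline. Other covariates are also available: baseline beliefs, assets and employment, and age, education and number of children from the administrative data. Only the outcome's own earlier value is missing.

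The gain may be small. The protocol's rationale says that women lose household status and that IPV often rises during and after pregnancy; both could weaken the correlation with endline. Pregnancy also makes baseline BMI a poor covariate.

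The choice of covariates belongs in an analysis plan, and detailed module content in the survey instrument. Neither is shown. That answers the question of how to adjust, but not the schedule that the protocol itself fixes.

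On cost, the grant is $74,707.60, or about $28 per woman ($74,707.60/2,640) for the whole study, so added fieldwork is not free. This is a reason to confine the request to short questionnaire modules.

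On hair cortisol, the protocol is open about the position: collection is funded, assay money will be sought, and samples keep for 1 to 2 years. The stress scale would still represent the domain.

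**Conclusion.** The point holds as a cheap improvement, not as a flaw that invalidates the trial. Empowerment, IPV and maternal anthropometry are primary, could be measured in month 2, and are scheduled only at month 13. The stress outcomes are scheduled nowhere.

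For counselling, the chance of an unseen starting difference above 0.2 SD is about 6% per domain at the assumed ICC of 0.05, and 0.7% to 17% over 0.02 to 0.10. The reduction in the 0.31 SD MDE runs from about 3%, if a correlation of 0.7 exists only within centres, to 0.22 SD if the same correlation holds at both levels. The documents do not say where in that range the trial lies.

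Two stronger readings are not supported. One is that adjustment is worth 33% to 96% more clusters: this takes r of 0.5 to 0.7 (1/(1 − r²) = 1.33 to 1.96), which has no source in the protocol, and requires it to hold between centres as well. The other is that hair cortisol will never be assayed: the protocol says only that laboratory funding is still to be sought. What can be said is that a primary outcome should not depend on funding unresolved at randomisation.

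**What to change.** 1. Add the empowerment, IPV and Cohen stress-scale modules to the month-2 face-to-face survey and mark them in Figure 1. MUAC is optional. No parental-investment baseline is needed for women without a child.
2. State that each of these primary analyses adjusts for its own baseline value.
3. Show the stress scale and hair sampling in Figure 1 with their months.
4. List hair cortisol as exploratory unless assay funding is committed before randomisation.

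The cost is a longer baseline interview at a visit already planned, with some added respondent burden and field time. No new visit is needed. Items 2 to 4 are changes to the text. Item 1 must be settled before the month-2 survey starts, because the values cannot be collected as a true baseline after allocation.

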7. ETHICAL CONSIDERATIONS

Ethical approval for this study will be obtained from the Human Research Ethics Committee (HREC) of the University of Sydney. Consents of local governments will be sought in study sub-districts through the sub-district administrations. Upon agreement with the local administration, the study will progress; the local administration will advertise about this study

to its members of the Kapsasia model through its own network before the research team make any contact to the potential study participants.

The participant information statement (PIS) will be translated to local language, namely Bengali, and a study team member or his/her representative will give the PIS to each eligible and selected study participant. The consent form will be read out to all potential participants who face difficulties in reading and writing, and a copy will be given to them so that the participants or his/her family members read and discuss it within the household before consenting to it. It will be ensured that the form is read out and given to potential participants at least a day prior to any survey visit.

We will obtain written informed consent from each study participant, which will be in Bengali. The PIS that we have prepared provides full disclosure regarding the study. The participants will be informed what does participation in this study involved and what they will need to do if they decide to participate. They will be informed that the participation in this study is entirely voluntary, and their decision to participate will not affect any government services that they currently receive. They will also be informed if participation involves any risk. The participants will be informed that they could drop out at any time without any penalty or loss of any benefits they currently receive under the Kapsasia Model.

We will strictly maintain the privacy, anonymity and confidentiality of the information that we will access through Kapsasia Model's digital data base, and any information that we will collect from the study participants. All information will be stored in encrypted database with all identifiers removed. Only associated investigators and data management team will have access to collected data. Findings will be published in peer-reviewed journals towards the end of the study.

8. SAFETY CONSIDERATIONS

Aside from giving up participants' time, we do not expect that there will be any considerable risks or disadvantages associated with taking part in this study. Nonetheless, the research team and field management staff will meet weekly via Zoom to manage trial coordination and oversee participant safety, study design, database integrity, and study conduct.

9. OUTCOMES

Our primary outcomes include measures of women's empowerment, parental investment, mother's physical and mental health, and intimate partner violence. Our secondary outcomes focus on the child and include measures of physical health and cognitive and socio-emotional development. We list the specific primary and secondary outcome variables below.

Primary outcomes: Women's empowerment (women's agency in fertility planning, personal expenditures and expenditures on children, children and household investment decisions, savings accounts, and participation in social programs and local leaderships); Women's beliefs (about importance of early life conditions, self-efficacy in parenting, beliefs about modifiability of child skills); Parental Investment (time, monetary, and warmth); Physical health (self-

reported physical health, body-mass index, and mid-upper arm circumference (MUAC)); Mental health (PHQ-9 a screener for depression, GAD-7 a screener for anxiety); IPV; and Stress (Cohen Stress Scale, Biomarkers of stress using hair samples³).

Secondary outcomes: Child's health at birth (birth weight and low birth weight); Developmental outcomes (Bayley Scales of Infant and Toddler Development that captures children's cognitive, language, motor, adaptive); Health (weight-for-length, length-for-age, acute respiratory illnesses); Stress (Biomarkers of stress from hair samples).

10. DATA MANAGEMENT

Data Capturing Method: In the baseline household survey (henceforth baseline), all interviews with participants will be conducted in-person face-to-face in the field. A local experienced and reliable survey firm will be recruited. Each participant will be compensated 150 Taka (about \$2 AUD) for their time if they participate in the baseline survey. The corresponding amounts for the midline telephone survey, and the endline face-to-face survey are 50 Taka and 150 Taka, respectively. Similarly, participants invited to take part in group meeting will be given 50 Taka per participant per meeting to cover their transportation cost. This compensation scheme is based on inputs received from local survey firms and study collaborators.

All primary surveys (baseline, midline, & endline) will be administered digitally using Qualtrics (or SurveyCTO conditional on its meets USyd privacy and security requirements) on Android Tablets. Once an enumerator marks a filled-out questionnaire as "finalized," the contents will be encrypted using an encryption key. From this point forward, the questionnaire can no longer be edited (not even the device that was used to complete the questionnaire will be able to decrypt it). Data will then be transmitted to the Qualtrics (SurveyCTO) server using 4G or another locally available Internet network, and the data will be encrypted in transit using SSL. From there, it will be downloaded by the research team the University of Sydney server (OneDrive (Enterprise) that the University of Sydney currently supports). When the data will be downloaded by the research team members, it will again be doubly encrypted by the key and SSL. A copy of the data will also be retained temporarily on the tablet until it is confirmed that the data is securely transmitted to the server, upon which the data retained in the tablets will be permanently deleted.

Data Quality Monitoring: A team led by one of the CIs will develop a data monitoring protocol, and the collected data will be regularly monitored to ensure its quality. This will be

³ We plan to collect biomarkers of stress from mothers and their infants. Using hair samples, we can extract HPA axis hormones such as cortisol. Hair-derived biomarker measurement indicates HPA axis activity over the course of months (analytes in each centimeter of hair approximate hormone secretion over one month), and thus more accurately reflect chronic hormone secretion (see Baranov et al. 2022 for a discussion and an example of successful hair cortisol measurement with mother and child dyads in Pakistan). Hair sample collection will be funded with this proposal but further funding will be sought for laboratory extraction of analytes. Hair samples are easily storable and stable for 1-2 years.

done in two steps – firstly, a small team independent of the survey firm will reinterview about 5% of the respondents selected randomly. This data will be matched with data collected by enumerators employed by the survey firm. Secondly, all field data will be matched with administrative data on key variables. Based on the above, a daily report will be generated specific to enumerator, which will be followed up by the field supervisors/ research assistants that we will employ.

Data Safety and Access to Data: All electronic data will be anonymized, encrypted, and stored at a secured server owned by the University of Sydney. The access to the server will be password protected and will be limited to the research investigators only. Similarly, all scanned copies of the consents will be similarly stored in a secured server, where access will be password protected, and only authenticated users will be allowed to access them. All hard copies of the consent forms stored in the local collaborator's office in Dhaka will be destroyed once the project is completed and it is no longer required to keep the hard copies.

All individual identifiers will be removed and will be replaced with codes, which would be used in case the research team plans to re-identify the participants. Such re-identification will be arranged with the Kapasia Model of Maternal and Child Health authority and will give the option to conduct long-term follow studies that track the effects of early intervention on human capital accumulations in adulthood. Such a study would be of significant interest to many policy makers and researchers alike.

Regarding the consents, which will be collected in papers, all the hard copies will be securely stored in the local collaborator's office in Dhaka. They will be scanned and electronically stored to the same server following the same procedure mentioned above.

The hard copies of the consent forms will be disposed once all of them are scanned, stored electronically, and the research has been completed. The electronic records of all materials will be deleted once the storage period requested in this application is over. Professional help from the IT manager at the School of Economics will be taken to ensure that the deleted records are not recoverable in any form.

Access to data will be restricted to the study investigators only and such access will be given through the University of Sydney server which will require password and user authentication. The secured access protocol will be further developed and monitored with the help of the IT at the School of Economics, University of Sydney.

